5.1.3 Concomitant medication date imputation

Concomitant medication (CMD) date imputation uses both a comparison of the partial CMD start date to the treatment start date, and the value of the CMDTYP1C flag (1, 2, or 3). Event date comparisons to treatment start date are made based on the year and month values only (any day values are ignored) in Table 1-3 below.

1. If the CMD start date year value is missing, the date will be imputed based on the CMDTYP1C flag value. If the flag value is 1 or 3, the imputed CMD start date is set to one day before the treatment start date. Else, if the flag value is missing or 2, the imputed CMD start date is set to one day after the treatment start date. (Note that for some legacy data, the CMDTYP1C variable may not exist in the data. When this happens and the CMD start date year value is missing, the imputed date value will be NULL.)
2. If the CMD start date year value is less than the treatment start date year value, the CMD started before treatment. Therefore:
 - a. if the CMD year is less than the treatment year and the CMD month is missing, the imputed CMD start date is set to the mid-year point (01JulYYYY).
 - b. Else if the CMD year is less than the treatment year and the CMD month is not missing, the imputed CMD start date is set to the mid-month point (15MONYYYY).

If the CMD start date year value is greater than the treatment start date year value, the CMD started after treatment. Therefore:

- a. If the CMD year is greater than the treatment year and the CMD month is missing, the imputed CMD start date is set to the year start point (01JanYYYY).
 - b. Else if the CMD year is greater than the treatment year and the CMD month is not missing, the imputed CMD start date is set to the month start point (01MONYYYY).
3. If the CMD start date year value is equal to the treatment start date year value:
 - a. and the CMD month is missing or the CMD month is equal to the treatment start month,
 - i. If the flag value is 1 or 3, the imputed CMD start date is set to one day before the treatment start date.

- ii. Else, if the flag value is missing or 2, the imputed CMD start date is set to one day after the treatment start date.
- a. Else if the CMD month is less than the treatment start month, the imputed CMD start date is set to the mid-month point (15MONYYYY).
- b. Else if the CMD month is greater than the treatment start month, the imputed CMD start date is set to the start month point (01MONYYYY).

Table 1-3: CMD date imputation

	MON MISSING	MON < CFM	MON = CFM	MON > CFM
YYYY MISSING	(F)	(F)	(F)	(F)
	Uncertain	Uncertain	Uncertain	Uncertain
YYYY < CFY	(D)=01JULYYYY	(C)=15MONYY	(C)=15MONYY	(C)=15MONYY
	Before Treatment Start	Before Treatment Start	Before Treatment Start	Before Treatment Start
YYYY = CFY	(B)	(C)=15MONYY	(B)	(A)=01MONYYYY
	Uncertain	Before Treatment Start	Uncertain	After Treatment Start
YYYY > CFY	(E)= 01JANYYYY	(A)=01MONYYYY	(A)=01MONYYYY	(A)=01MONYYYY
	After Treatment Start	After Treatment Start	After Treatment Start	After Treatment Start
Before Treatment Start		Partial indicates date prior to Treatment Start Date		
After Treatment Start		Partial indicates date after Treatment Start Date		
Uncertain		Partial insufficient to determine relationship to Treatment Start Date		
LEGEND:				
(A)	MAX(01MONYYYY,TRTSTD+1)			
(B)	IF CMDTYP1C IN (1,3) THEN TRTSTD-1 ELSE IF CMDTYP1C in(. , 2) THEN TRTSTD+1			
(C)	15MONYYYY			
(D)	01JULYYYY			
(E)	01JANYYYY			
(F)	IF CMDTYP1C IN (1,3) THEN TRTSTD-1 ELSE IF CMDTYP1C in (. , 2) THEN TRTSTD+1			

5.2 AEs coding/grading

The verbatim term recorded on CRF will be identified as adverse event and will be coded by primary system organ class and preferred term using Medical Dictionary for Regulatory Activities (MedDRA) version 20.1 and above.

5.3 Laboratory parameters derivations

Not applicable

5.4 Statistical models

This is an open-label single arm safety trial for patients and the data will be presented in descriptive manner.

5.5 Rule of exclusion criteria of analysis sets

All protocol deviations defined at the start of the study are listed with associated population codes in below table. The list will be updated before CDBL.

Protocol Deviation ID	Protocol Deviation Description	Population code
I01	Written informed consent was not obtained before performing any assessment.	1
M01	Patient took prohibited concomitant medication	0
E01	Pregnant or nursing female patients, where pregnancy is defined as state of a female after conception and until termination of gestation, confirmed by +ve hCG laboratory test or urinary pregnancy test	0
S01	Canakinumab not administered as per protocol dosage different than 2mg/kg or 4 mg/kg	0
S02	Canakinumab not administered per protocol schedule. Difference between the dose on consecutive visits (dd-mmm-yyyy) and (dd-mmm-yyyy) is not between 6 weeks to 8 weeks.	0
	No treatment is taken.	1

6 Reference

Clinical Study Protocol CACZ885G2301E1: An open-label extension study of canakinumab (ACZ885) in patients with Systemic Juvenile Idiopathic Arthritis (SJIA) and active systemic manifestations who participated in studies ACZ885G2301 and ACZ885G2305; and response characterization study in canakinumab treatment-naïve patients with active SJIA with and without fever

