1.2 Study objectives and endpoints

The objective of this protocol is to collect additional safety data (serious and non-serious adverse events) and to provide continuous Ilaris® (canakinumab) treatment to patients in France who completed CACZ885G2301E1, CACZ885N2301 or CACZ885G2306 study.

The end of study is defined as premature termination or end of the study according to protocol: in the month following the availability of repaid product in France.

Visits will take place at scheduled administration date every 4, 6, 8 or 12 weeks (section 5). If no visit is performed within 12 weeks of previous injection, a control visit will be performed at week 13 +/- 7 days after the last administration in order to evaluate safety and need for the patient to continue the treatment and study.

Patients may voluntarily withdraw from study for any reason at any time. If premature withdrawal occurs, the investigator must make every effort to complete End of study visit in the CRF and to determine the primary reason for patient's premature withdrawal from the study and record this information.

2 Statistical methods

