2.4 Treatments (study treatment, rescue medication, concomitant therapies, compliance)

2.4.1 Study treatment / compliance

The maximal total single dose of canakinumab (ACZ885) allowed is 300 mg, which is administered as two subcutaneous 150 mg injections once every 4 weeks.

The canakinumab dose interval (i.e. every 6, 8 or 12 weeks) may also be prolonged in patients with adequate response according to the clinical response and investigators judgment.

The extent of exposure will be examined to determine the degree to which safety can be assessed for canakinumab (ACZ885). The extent of exposure to study drug will be characterized according to the duration of exposure and the number of patients exposed.

Duration of exposure to the treatment will be calculated as the number of days between the first dose date and the last dose date exposed to that treatment over the specified period in Ilaris (ACZ885GRR01) study, expressed as: Duration of exposure = ((Date of last known dose of study drug – Date of first dose of study drug) – Number of days interrupted) + 1.

The duration of exposure (in days) and the cumulative volume administered (in mL) will be summarized with descriptive statistics (n, mean, median, standard deviation, minimum, maximum, Q1, Q3) for the safety set.

The total number of doses (injections) administered, number of 2 mg/kg doses administered, number of 4 mg/kg doses administered will be summarized with number and percentage for overall, 2mg/kg and 4 mg/kg dose group for safety set. By subject listing along with dose date will be provided for safety set.

The duration of exposure (in days) and number of injection will be summarized for the safety set as

- a continuous variable with the standard descriptive statistics
- a categorical variable for number of does (injections) administered classified into 1-4, 5-8, 9-12, 13-16, 17-20, 21-24 with number and percentage for below group.
 - Number of doses (injections) administered
 - Number of 1 mg/kg q4w doses administered
 - Number of 2 mg/kg q4w doses administered
 - Number of 4 mg/kg q4w doses administered
 - Number of 2 mg/kg q8w doses administered
 - Number of 4 mg/kg q12w doses administered
 - Other dose administered
 - No dose administered
- Number of subject and percentage at baseline, reduction in dose at end of study, increase in dose at end of study and stable dose with all dose amount.

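### As written, SAP deviation codes S01 and S02 count canakinumab doses and intervals that the protocol permits as protocol deviations

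*SAP*

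**What the plan says.** SAP 5.5 lists the deviations defined at the start of the study, each with a population code. S01 reads "Canakinumab not administered as per protocol dosage different than 2mg/kg or 4 mg/kg". S02 opens with "Canakinumab not administered per protocol schedule" and then states its test: "Difference between the dose on consecutive visits (dd-mmm-yyyy) and (dd-mmm-yyyy) is not between 6 weeks to 8 weeks". Both have code 0, which SAP 2.2 defines as no exclusion. Of the list as a whole the SAP says: "The list will be updated before CDBL". SAP 2.3.2 counts patients, with percentages, by deviation category and deviation, and lists each deviation.

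The dosing rules elsewhere are wider.

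- **Intervals.** Protocol section 6 (footnote 4 to the visit table) and SAP 1.2 both schedule dosing at 4, 6, 8 or 12 weeks. The footnote also allows longer gaps at the investigator's discretion.
- **Regimens.** Protocol section 5 gives 2 or 4 mg/kg every 4 weeks, capped at 150 or 300 mg, for CACZ885G2301E1 patients. CACZ885N2301 patients receive 150 or 300 mg (2 or 4 mg/kg at 40 kg or less) every 4 or 8 weeks. CACZ885G2306 patients receive 1, 2 or 4 mg/kg every 4 weeks, or 4 mg/kg every 8 or 12 weeks.
- **Changes.** Protocol 5.5.5 leaves dose adjustment and interruption to the investigator.
- **SAP exposure section.** SAP 2.4.1 gives a maximal single dose of 300 mg, "which is administered as two subcutaneous 150 mg injections once every 4 weeks", and plans rows for "Number of 1 mg/kg q4w doses administered" and "Number of 4 mg/kg q12w doses administered".

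**The concern.** The SAP codes as deviations some of the same dosing that it plans to tabulate as ordinary exposure. Four-weekly dosing is the basic schedule for all three parent studies, and it fails the S02 test even when every injection is on time. If the two tests were programmed as printed, the deviation table in the study report would show compliant patients as dosing deviators. Some real, unplanned delays in four-weekly dosing would not appear. A reader could not use the table to judge how closely dosing followed the protocol.

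**Working it through.** There is no plan figure to reproduce: the study is descriptive and has no sample size calculation. The check applies the two printed tests to the permitted dosing.

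**S02, inputs.** The pass range is 6 to 8 weeks, taken as inclusive: 6 × 7 = 42 to 8 × 7 = 56 days. The permitted intervals are 4, 6, 8 and 12 weeks. The visit window is ±7 days (protocol section 6), measured here from the previous dose.

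| Interval | Nominal gap | S02 at nominal | Window (days) | In-window days flagged |
|---|---|---|---|---|
| 4 weeks | 28 | flagged | 21–35 | 15 of 15 |
| 6 weeks | 42 | passes | 35–49 | 7 of 15 (35–41) |
| 8 weeks | 56 | passes | 49–63 | 7 of 15 (57–63) |
| 12 weeks | 84 | flagged | 77–91 | 15 of 15 |

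These are gap lengths, not doses or patients. The visit table does not say where the window is anchored. If it sits around fixed scheduled visits, the gap between two in-window visits can range over the interval ±14 days. The flagged gap lengths are then 28 of 29, 14 of 29, 14 of 29 and 29 of 29, so the conclusion does not depend on the anchor.

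**S02, by regimen.** Protocol section 5 lists 2 + 4 + 5 = 11 regimen entries for the three parent studies. Seven are four-weekly (2 + 2 + 3) and one is twelve-weekly. S02 flags these 8 of 11 when given exactly on time; the three eight-weekly entries pass.

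**S02, missed delays.** A patient due every 28 days passes S02 at any gap from 42 to 56 days, which is 42 − 28 = 14 to 56 − 28 = 28 days late. That is a missed deviation only if no investigator decision lies behind the delay.

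**S01.** The test accepts 2 and 4 mg/kg only.

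- 1 mg/kg every 4 weeks, listed in protocol section 5 and tabulated in SAP 2.4.1, fails. It also fails S02.
- A flat 150 mg equals 2 mg/kg, and a flat 300 mg equals 4 mg/kg, only at 150/2 = 300/4 = 75 kg. At an assumed 50 kg they are 150/50 = 3.0 and 300/50 = 6.0 mg/kg. Read literally, S01 flags these permitted doses for CACZ885N2301 patients over 40 kg.
- Capped doses fail above 75 kg. At an assumed 80 kg, 150 mg is 1.88 and 300 mg is 3.75 mg/kg.

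**Reach.** S01 and S02 are both code 0, so nobody leaves the safety set. Adverse event and exposure summaries use that set and do not use the codes.

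**The case against.** The strongest reply is that the opening words of each code, which refer to dosing not given per protocol, are the real criterion. On that view the date placeholders in S02 show listing text rather than a finished algorithm. The list is also due for revision before lock, and SAP 2.4.1 lists dose dates by subject, so a false flag could be spotted. This makes a correction likely and easy. It does not make the printed tests right: they are the only checkable content of the two rows, they contradict the protocol schedule, and a promised update is not a correction.

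A second reply is that a 42- to 56-day gap is itself a permitted interval, since prolongation and interruption are at the investigator's discretion. That stands. The missed-delay limb applies only to undirected delays, and the documents do not show how often these occur.

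Three stronger readings are tempting and unsupported.

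- A reader might infer that the safety results are distorted. Population code 0 rules that out.
- A reader might infer that S01 touches only the 1 mg/kg regimen and so at most the 21 CACZ885G2306 patients foreseen in protocol section 4. A literal S01 also reaches flat and capped doses in the other groups, and those 21 include patients on other regimens. So 21 is neither a count nor a valid ceiling.
- A reader might infer that the final deviation table will be wrong. That requires the tests to be programmed literally and left uncorrected at the planned update.

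**Conclusion.** The point holds, and it is minor. Both codes are wrong as written: S02 rejects punctual 4- and 12-week dosing and part of the 6- and 8-week windows, and S01 rejects 1 mg/kg and, literally, flat and capped doses. The harm is confined to the deviation table and listing of SAP 2.3.2. The conclusion assumes that the printed tests are applied as they stand and that the 6-to-8-week limits are inclusive; the day counts for the 6- and 8-week windows also assume a window measured from the previous dose. No patient number can be given, because the documents contain no distribution of patients by regimen, interval or weight.

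**What to change.** Replace the two rows at the list update already planned before lock.

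- **S01:** flag a dose that differs from the dose prescribed on the Dosage Administration Record, or that exceeds the protocol maximum (300 mg, or 4 mg/kg for patients of 40 kg or less). Do not flag 1, 2 or 4 mg/kg, flat or capped 150 or 300 mg, or investigator-directed adjustments under protocol 5.5.5.
- **S02:** flag a dose given more than 7 days from the date due under the interval in force for that patient (4, 6, 8 or 12 weeks). Exclude investigator-directed prolongation, including beyond 12 weeks, and interruption. State whether the due date is counted from the previous dose or from the scheduled visit.

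The cost is two table rows and two reprogrammed checks, plus possible data queries. Protocol 5.5.4 and 6.2 name prescribed and dispensed dosages, dose changes, injection dates and volumes, but not the planned interval. The visit schedule lists no weight measurement. Both items may have to be obtained from sites for the checks to run.
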